7.2 Exclusion criteria

- Male sex
- Young age (< 40 years) and older age (> 65 years)
- Pregnant women
- Puerperium women (up to 40 days post-partum)
- Women who had undergone urinary and gynecology surgery

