4. OUTCOMES

Primary outcome

- Prevalence of middle-aged women with urinary incontinence.

Secondary outcomes

- Description of UI and related predictors, quality of life, social impact and costs.
- Association between UI and related predictors, quality of life, social impact and costs.

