5. EXPECTED RESULTS

The collection of data and information through this study will aim to:

- a) Understand the percentage of middle-aged women with UI.

 
I.R.C.C.S. Ospedale San Raffaele
	
STUDY PROTOCOL
	
WUIPS Version n. 1 23.08.2023

---	------------------------------	---

- b) Describe the socio-demographic and clinical characteristics of women with UI.
- c) Identify UI predictors.
- d) Describe the quality of life, social impact and costs of women with UI.

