8. PARTICIPANT REGISTRATION

Data collection will be carried out through the use of two questionnaires validated in Italian language and a survey built by the researchers on the basis of the scientific literature.

Two different paths have been designed to recruit participants, depending on whether they are female personnel or female patients and female caregivers:

 
I.R.C.C.S. Ospedale San Raffaele
	
STUDY PROTOCOL
	
WUIPS Version n. 1 23.08.2023

---	------------------------------	---

- for healthcare professionals and administrative workers of the four hospitals, one week before the administration of the data collection tools (a survey and two validated questionnaires), an email will be sent to the work account to present the topic and the aim of the study. A second email will then be sent with a link to access the online survey/questionnaires (RedCap) and with a deadline by which to fill it out. The email will be sent to all workers, asking for the compilation only to women of 40-65 age range group and who meet the inclusion criteria. Participants will agree to a brief privacy policy and electronic release of informed consent before completing the survey and the questionnaires.
- for female patients and female caregivers' registration, participants will be recruited at the central admission and at the private admission of four hospitals in Northern Italy. At recruitment, inclusion and exclusion criteria will be evaluated through a brief preliminary interview, lasting about a couple of minutes. It will take place immediately before the administration of the questionnaires at the central and private reception of the hospitals involved. On this occasion, a researcher in charge of data collection will ask the participant for information on: age, pregnancy/puerperium status and past history of gynecological surgery. Each participant who joins the study will be provided with a paper module, containing the survey and the questionnaires, marked with a progressive identification number: after signing the informed consent, all participants will be asked to answer questions voluntary and anonymously at the moment and return the completed module to researchers.

Data will be collected anonymously by a paper module for patients and caregivers and by RedCap for healthcare professionals and administrative workers. Then, the data on the platform will be extracted to the eCRF; the paper data will be uploaded to the eCRF by the researchers.

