9. DATA COLLECTION

All the data will be collected based on a series of variables which derive from an accurate narrative review of the UI predictors, costs and quality of life of the women affected by the problem (Danforth et al., 2006; Datar et al., 2022; Goren et al., 2014; Harding et al., 2023; Sensoy et al., 2013). These variables are described in Table 1. The obtained information will be gathered in the eCRF, which the investigators will only access during the analyses and synthesis of data.

Table 1 - Outcome and description of the investigated variables

OUTCOME	VARIABLE	DESCRIPTION
UI predictors	Age	The prevalence of UI seems strongly related to the age of the woman and specifically prevalence figures increase with increasing age (Milsom & Gyhagen, 2019)

	Ethnicity	The risk of SUI appears to be lower in black and Asian-American women compared to white women (Danforth et al., 2006; Thom et al., 2006)
	Scholarship	According to some studies (Batmani et al., 2021; Marques et al., 2015), increasing the level of education is an important factor in reducing the incidence of urinary incontinence
	Body Mass Index (BMI)	There is evidence that the prevalence of both UUI and SUI increases proportionately with BMI (Harding et al., 2023)
	Comorbidities	
Lower urinary tract symptoms are associated with multiple comorbid conditions including:
 
 • cardiac failure • chronic renal failure • chronic obstructive pulmonary disease • diabetes • hypertension • metabolic syndrome • pelvic organs prolapse • urinary tract infections • bowel disorders (constipation, irritable bowel syndrome) • sleep disturbances • depression • neurological disease • general cognitive impairment 
(Batmani et al., 2021; Harding et al., 2023; Sensoy et al., 2013; Wang et al., 2010)

	Pelvic or uro-gynecological surgery	Other factors positively associated with SUI include previous pelvic or uro-gynecological surgery (Ellström Engh et al., 2006; Harding et al., 2023)

	Menopause	Menopausal status seems to influence the onset and characteristics of urine leakage (Sensoy et al., 2013; Thangarajah et al., 2020)
	Parity	Pregnancy and childbirth are triggers for SUI (Li et al., 2023; Bortolotti et al., 2000)

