9.1.1 UI Survey

A survey, written in Italian by the authors, will collect women's socio-demographic, economic and clinical characteristics, based on the variables reported in Table 1. The entire survey is attached in Appendix.

 
I.R.C.C.S. Ospedale San Raffaele
	
STUDY PROTOCOL
	
WUIPS Version n. 1 23.08.2023

---	------------------------------	---

A total of 29 questions will attempt to acquire information about some of the previously defined variables: specifically, 23 questions will be related to socio-demographic and clinical predictors of UI (n. 1-23), one question will be about the onset of the UI symptomatology (n. 35), one question about sexuality (n. 36) and four questions will investigate the direct and indirect costs of UI (n. 37-40). The survey was tested as a pilot on a sample of 13 women aged between 40 and 65 years old and was assessed as suitable for the following aspects: understanding and clarity of the questions, absence of questions that put the participant in difficulty, completion time (which resulted maximum of 5 minutes).

9.1.2 International Consultation of Incontinence Modular Questionnaire Urinary Incontinence Short Form (ICIQ UI-SF)

The International Consultation of Incontinence Modular Questionnaire Urinary Incontinence Short Form (ICIQ UI-SF) is a questionnaire that allows the assessment of the prevalence, frequency, and perceived cause of UI and its impact on everyday life. It is an appropriate scale for estimating national prevalence in representative samples (Bedretdinova et al., 2015).

ICIQ UI-SF was developed and validated in English for the first time by Avery and colleagues in 2004, and then Tubaro and colleagues made an Italian Validation in 2006. This last version will be used in the study.

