APPENDIX

UI SURVEY – SCHEDA di RACCOLTA DATI

Gentilissima, nel ringraziarla per aver accettato di contribuire a questa ricerca, la invitiamo a rispondere alle domande di seguito, di natura clinica e socio-demografica, con le quali indaghiamo alcuni fattori che potrebbero essere predisponenti all'insorgenza di una condizione nota come incontinenza urinaria.

1. Indichi il suo anno di nascita:

--	--	--	--

2. Indichi la sua nazionalità:

1. Italiana
 2. Straniera (specificare _____)

3. Indichi la regione di domicilio:

- 1. Lombardia
- 2. Altra regione (specificare _____)

4. Se è domiciliata in Lombardia, indichi la provincia del suo domicilio:

 1. Bergamo	 5. Lecco	 9. Monza
 2. Brescia	 6. Lodi	 10. Pavia
 3. Como	 7. Mantova	 11. Sondrio
 4. Cremona	 8. Milano	 12. Varese

5. Indichi il suo peso in chili:

--	--	--

6. Indichila sua altezza in centimetri

10 cm

7. Indichi il grado massimo di studi raggiunto (scolarità):

- 1. Educazione primaria (elementari, medie)
- 2. Educazione secondaria o avanzata (diploma di istituto professionale, tecnico o liceo, laurea)

8. Soffre o ha mai sofferto di una delle seguenti patologie? (Può indicare anche più di una risposta):

- 1. Insufficienza cardiaca
- 2. Insufficienza renale cronica
- 3. Broncopneumopatia cronico-ostruttiva (BPCO)

- 4. Diabete
- 5. Ipertensione
- 6. Sindrome metabolica
- 7. Prollasso vescicale / vaginale / rettale
- 8. Infezione ricorrente delle vie urinarie
- 9. Sindrome da intestino irritabile
- 10. Stipsi
- 11. Disturbi del sonno
- 12. Depressione
- 13. Patologia neurologica
- 14. Disabilità cognitiva generale
- 14. Altro (specificare: _____)

9. Ha mai subito interventi di chirurgia ginecologica e/o urologica?

- 1. Sì
- 2. No

10. Se alla domanda precedente ha risposto Sì, specifichi quale/i intervento/i ha subito:

11. In quale stato menopausale si definirebbe?

- 1. In pre-menopausa
- 2. A inizio menopausa
- 3. In post-menopausa

12. Ha figli?

- 1. Sì
- 2. No

13. Se alla domanda precedente ha risposto Sì, indichi il numero di figli:

- 1
- 2
- ≥ 3

14. Indichi l'anno di nascita dell'ultimo figlio

--	--	--	--

15. Quanti parto per via vaginale ha avuto?

- 0
- 1
- 2
- ≥ 3

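### Section 7.2 excludes women with prior urinary or gynaecological surgery, while Table 1 and survey questions 9-10 treat that same history as a predictor of UI, so its association cannot be estimated

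*Protocol*

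**What the plan says.** The exclusion list in Section 7.2 contains "Women who had undergone urinary and gynecology surgery", with no time limit and no list of operations.

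Table 1 in Section 9 has a row for pelvic or uro-gynaecological surgery under the heading of UI predictors, with the reason: "Other factors positively associated with SUI include previous pelvic or uro-gynecological surgery".

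The survey in the Appendix asks at question 9 "Ha mai subito interventi di chirurgia ginecologica e/o urologica" (any gynaecological and/or urological operation, ever). For women who answer Yes, question 10 adds "specifichi quale/i intervento/i ha subito" (which operation or operations). Section 9.1.1 assigns questions 1 to 23, and so both of these, to the predictors of UI.

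The predictors have a stated use. Section 4 lists as a secondary outcome "Association between UI and related predictors, quality of life, social impact and costs", and Section 5 lists among the expected results "Identify UI predictors".

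On screening, Section 8 says that for patients and caregivers "inclusion and exclusion criteria will be evaluated through a brief preliminary interview". The information it then lists covers age, pregnancy or puerperium, and earlier gynaecological operations. Staff are reached by e-mail, which asks women in the age range who satisfy the inclusion criteria to respond. No interview or surgery question before the survey is described for them.

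**The concern.** A predictor can be studied only if some participants have it and some do not. Section 7.2 appears to remove the women who have it, while Table 1, questions 9-10 and the secondary outcome assume that they are present. If the protocol is followed, this part of the secondary outcome has no data. A later analysis plan cannot repair this, because the women concerned would never have been enrolled. If the protocol is followed imperfectly, the only women who report surgery are those who should not be in the sample, and an association computed from them would reflect screening errors.

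The reader also needs to know whether women who have had such surgery are in the denominator of the reported prevalence.

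**Working it through.** No figure in the protocol is contested here, so the check sets the sections side by side.

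**1. Meaning of 'and' in Section 7.2.** The age bullet in the same list joins under 40 and over 65 with 'and'. No woman can be both, so 'and' in that bullet means that either condition excludes. The surgery bullet is most naturally read the same way.

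**2. Consequence for question 9.** There are four possible histories: no such surgery, gynaecological only, urological only, or both. Under the 'either' rule only the first is eligible. Question 9 joins the two types with and/or, so the answer is Yes for each of the other three and No for the first. Among eligible women, question 9 is therefore always No and question 10 is always blank.

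**3. Consequence for the association.** Let *a* and *b* be the numbers with and without UI among women who report surgery, and *c* and *d* the same among women who do not.
- Prevalence difference = *a*/(*a*+*b*) − *c*/(*c*+*d*). With *a* = *b* = 0 the first term is 0/0 and is undefined.
- Odds ratio = *ad*/(*bc*) = 0/0, also undefined.
- In a regression model the variable is constant and its coefficient cannot be estimated.

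This holds at any sample size and any UI prevalence.

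**4. Does the word 'pelvic' in Table 1 rescue the predictor?** No. Pelvic surgery outside gynaecology and urology would not be excluded by Section 7.2, but question 9 does not ask about it.

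**5. Screening as listed.**

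| Place | Surgery named |
|---|---|
| Section 7.2 | urinary, gynaecological |
| Section 8, interview items | gynaecological only |
| Section 8, staff e-mail | none stated |
| Question 9 | gynaecological and/or urological |

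If the interview were confined to its listed items, a patient with urological surgery only would not be identified there. For staff, the first question about surgery that the protocol describes is question 9 itself.

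**The case against.** **Question 9 may double as an eligibility check.** Question 1, year of birth, serves both a predictor and an eligibility criterion, so question 9 could too, particularly online. The protocol does not say so. If it were used that way, every woman who answered Yes would be removed and the predictor would again be constant. The conflict remains.

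**'And' might mean both types of surgery.** Women with one type would then be eligible and question 9 could vary, with the predictor truncated rather than empty. The age bullet makes this reading weak, and nothing else in the protocol supports it.

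**The screening gaps may be gaps of wording only.** This objection largely stands. The interview is said to cover the inclusion and exclusion criteria, and its listed items also omit understanding of Italian, which is an inclusion criterion, so the list may not be exhaustive. Section 6 makes meeting the inclusion criteria the condition for every participant, although exclusions clearly apply as well. The phrase is therefore probably shorthand for eligibility.

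A reader might infer more: that staff are admitted whatever their surgical history, that prior surgery will therefore be tied to recruitment route, or that the prevalence is biased by some amount. The documents do not support this. The first two inferences need a literal reading that Section 6 undercuts. For the third, the protocol gives neither the share of women with such surgery nor their UI rate. The 1,842 female employees in Section 11 are staff aged 40-65 at two hospitals, not respondents and not women with a surgical history, so they measure no effect.

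**Conclusion.** The contradiction is in the text and no section reconciles it. With 'and' in Section 7.2 read as 'either', the surgery predictor is constant among eligible women and its association with UI cannot be estimated. The loss is one listed predictor within one secondary outcome. This part is held with high confidence.

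The omission of urinary surgery from the listed interview items, and the absence of a described surgery screen for staff, are secondary points held with moderate confidence. No size or direction of effect on the primary prevalence is claimed. The matter should be corrected before enrolment, since afterwards the missing women cannot be recovered.

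**What to change.** Before enrolment, reconcile Sections 7.2, 8, 9 (Table 1) and 9.1.1 and the Appendix with one definition of surgery, for example the existing and/or wording of question 9. The sponsor then chooses one of two options.

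**(a) Drop the exclusion.** Remove the surgery bullet from Section 7.2 and the surgery item from the interview in Section 8. Analyse questions 9-10 as the predictor, and word the Table 1 row to match question 9. Report prevalence overall and also restricted to women who answer No to question 9. The survey and its question counts do not change. The cost is a more heterogeneous sample and one added analysis.

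**(b) Keep the exclusion.** Word it as in question 9 and remove surgery from the Table 1 predictors. Apply the same question as an eligibility check on both routes: in the interview, and at the start of the online form for staff. Describe the reported prevalence as applying to women without such surgery. The cost is one lost predictor and a narrower population.

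Option (b) must also say whether question 10 is kept or dropped, and correct Section 9.1.1. That section now counts 23 + 1 + 1 + 4 = 29 questions. With questions 9 and 10 no longer predictors, 23 becomes 23 − 2 = 21. The total then depends on what is kept:
- both stay in the survey as eligibility items: 21 + 2 + 1 + 1 + 4 = 29;
- only question 9 stays: 21 + 1 + 1 + 1 + 4 = 28;
- neither stays in the survey: 21 + 1 + 1 + 4 = 27.

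If items are renumbered, the question numbers cited in Sections 9.1.1, 9.1.2 and 9.1.3 need updating.

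Either option is one short amendment, shared with the Ethics Committee as Section 14 provides. Neither needs a new data item.

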8. PARTICIPANT REGISTRATION

Data collection will be carried out through the use of two questionnaires validated in Italian language and a survey built by the researchers on the basis of the scientific literature.

Two different paths have been designed to recruit participants, depending on whether they are female personnel or female patients and female caregivers:

 
I.R.C.C.S. Ospedale San Raffaele
	
STUDY PROTOCOL
	
WUIPS Version n. 1 23.08.2023

---	------------------------------	---

- for healthcare professionals and administrative workers of the four hospitals, one week before the administration of the data collection tools (a survey and two validated questionnaires), an email will be sent to the work account to present the topic and the aim of the study. A second email will then be sent with a link to access the online survey/questionnaires (RedCap) and with a deadline by which to fill it out. The email will be sent to all workers, asking for the compilation only to women of 40-65 age range group and who meet the inclusion criteria. Participants will agree to a brief privacy policy and electronic release of informed consent before completing the survey and the questionnaires.
- for female patients and female caregivers' registration, participants will be recruited at the central admission and at the private admission of four hospitals in Northern Italy. At recruitment, inclusion and exclusion criteria will be evaluated through a brief preliminary interview, lasting about a couple of minutes. It will take place immediately before the administration of the questionnaires at the central and private reception of the hospitals involved. On this occasion, a researcher in charge of data collection will ask the participant for information on: age, pregnancy/puerperium status and past history of gynecological surgery. Each participant who joins the study will be provided with a paper module, containing the survey and the questionnaires, marked with a progressive identification number: after signing the informed consent, all participants will be asked to answer questions voluntary and anonymously at the moment and return the completed module to researchers.

Data will be collected anonymously by a paper module for patients and caregivers and by RedCap for healthcare professionals and administrative workers. Then, the data on the platform will be extracted to the eCRF; the paper data will be uploaded to the eCRF by the researchers.

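### Exclusion criteria are checked for patients and caregivers but no check is described for staff, and the form cannot show current pregnancy and shows the puerperium only crudely

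*Protocol*

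**What the plan says.** Section 7.2 lists the exclusions once, for the whole study. They include "Pregnant women", women in the puerperium (up to 40 days after delivery) and "Women who had undergone urinary and gynecology surgery". None of these appears in the inclusion list of section 7.1, whose entry for employees asks only that they be female workers of the four hospitals.

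Section 8 then sets out two recruitment paths.

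- Patients and caregivers: "At recruitment, inclusion and exclusion criteria will be evaluated through a brief preliminary interview, lasting about a couple of minutes". The researcher asks about "age, pregnancy/puerperium status and past history of gynecological surgery".
- Staff: an e-mail goes to all workers, "asking for the compilation only to women of 40-65 age range group and who meet the inclusion criteria". An online link, a privacy notice and electronic consent follow. No interview or screening question is described.

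Section 9.1 gives both groups the same materials, on paper or online. In the Appendix, the item closest to the puerperium is question 14: "Indichi l'anno di nascita dell'ultimo figlio". Question 1 asks for year of birth. Questions 9 and 10 ask about gynaecological and/or urological surgery and its type. Sections 8 and 16 state that data are collected anonymously.

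**The concern.** The primary outcome in section 4 is a single prevalence over everyone enrolled, so it combines two groups whose eligibility is checked differently. A pregnant employee satisfies every criterion that the e-mail, as described, asks her to apply. The same woman at the admission desk would be screened out.

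Three things are at stake. First, the denominator would not be the population that section 7 defines; item 10 of the protocol's own risk-of-bias tool (Table 3) asks about exactly this. Second, Table 1 names pregnancy and childbirth as provoking stress incontinence, so the women let through need not resemble the rest. Third, an analysis plan cannot recover pregnancy status if it was never collected and respondents cannot be traced.

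**Working it through.** **Step 1. Each exclusion against the two paths and the form**

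| Exclusion (7.2) | Desk interview (8) | Staff path (8) | Form item | Identifiable afterwards? |
|---|---|---|---|---|
| Age outside 40-65 | Asked | Named in e-mail | Q1, year of birth | Yes, to within a year |
| Pregnancy | Asked | Not named | None | No |
| Puerperium, 40 days | Asked | Not named | Q14, year of last birth | Only crudely |
| Gynaecological surgery | Asked | Not named | Q9/Q10 | Yes |
| Urinary surgery | Not listed | Not named | Q9/Q10 | Yes |

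On the puerperium row: a woman within 40 days of the birth of a living child must report the current or the previous calendar year at Q14. Dropping both years would remove such women together with eligible women who delivered earlier in that period. Q14 says nothing about a current pregnancy.

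**Step 2. Size for pregnancy and puerperium**

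The protocol states no figure to reproduce. Inputs from section 11: 1,842 female staff aged 40-65 at two of the four hospitals; UI prevalence of 10.2% in one Italian study and 25-45% in most studies. Assumptions, not in the protocol: a share *f* of 0.5-2% of staff pregnant or puerperal, and a UI prevalence *d* of 20-30 points above that of eligible staff.

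- Women affected: 1,842 × 0.005 = 9; 1,842 × 0.02 = 37 (if all employees respond).
- Shift in staff prevalence = *f* × *d*: 0.5% × 20 = 0.1 point; 2% × 30 = 0.6 point.

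For comparison, the 95% half-width is 1.96 × √[p(1−p)/1,842]:

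- p = 10.2%: 1.4 points
- p = 25%: 2.0 points
- p = 45%: 2.3 points

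A wider set of assumptions, with *f* = 0.5-3% and UI prevalence of 30-70% in the affected women, gives shifts of *f* × (p_affected − p):

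- p = 10.2%: +0.1 to +1.8 points
- p = 25%: 0.0 to +1.4 points
- p = 45%: −0.5 to +0.8 points

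Of these, only shifts near the extreme corner (3% share, 70% among them, 10.2% otherwise) exceed the half-width: 3% × (70 − 10.2) = 1.8 against 1.4. In the pooled estimate the shift is multiplied by the staff fraction of the sample, so it is smaller still.

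**Step 3. Surgery, as a separate matter**

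If 10-30% of staff had such surgery (assumed), that is 1,842 × 0.10 = 184 to 1,842 × 0.30 = 553 women. With an assumed 10-point difference in UI, keeping them shifts staff prevalence by 10% × 10 = 1.0 to 30% × 10 = 3.0 points. These women are recorded through Q9/Q10. Whether they stay in depends on a rule that the protocol does not state, not on missing data.

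**The case against.** The strongest reply is that the rule itself is uniform. Section 6 uses the same phrase about meeting the inclusion criteria for all four groups, including the patients and caregivers to whom section 8 plainly applies the exclusions. The phrase may be shorthand for the whole of section 7. A pregnant employee is excluded under 7.2 whichever path she takes, so the defect lies in the checking. That stands, and it rules out saying that she takes part validly under the plan. It does not supply a check for staff or an item that would reveal her.

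The text of the e-mail and the consent screen is also not shown, and some staff may exclude themselves. So excluded women *can* enter; the document does not show that they will.

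A reader might infer that all excluded staff are beyond removal, and count the 184-553 women with surgery among them. The form contradicts this: age and surgery are both recorded, and recent births can be flagged conservatively. Only current pregnancy leaves no trace at all.

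A reader might also infer that a comparison of staff with patients and caregivers is spoiled. Sections 4 and 13 plan no such comparison. Nor is the desk interview a complete standard, since its listed questions omit urinary surgery. The lack of a question on sex matters little, as the request is addressed to women.

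**Conclusion.** The point holds as an eligibility and consistency defect. Section 7.2 covers everyone, section 8 describes a check of the exclusions for one path only, and the form cannot identify current pregnancy and identifies the puerperium only by calendar year.

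The numerical effect of pregnancy and puerperium is probably small: 0.1 to 0.6 points in staff prevalence, below the 1.4 to 2.3 point half-width at 1,842 respondents. This rests on an assumed share and an assumed excess that the protocol does not supply. With fewer respondents the half-width grows, while the shift depends on the share alone.

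Surgery could matter more, but for a different reason. Section 7.2 excludes it, the desk interview asks about part of it, Q9/Q10 record it for everyone, and Table 1 lists it as a predictor to be studied. These places do not agree, and no rule says what happens to a respondent who answers yes.

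The point merits action despite its modest size because pregnancy status in anonymous forms cannot be repaired after collection.

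**What to change.** 1. Use one identical eligibility checklist in both paths: age 40-65, current pregnancy, delivery in the last 40 days, and gynaecological and urinary surgery as section 7.2 is finally worded.
2. For staff, place it before the RedCap form and end the form on an excluding answer. For patients and caregivers, use the same list as the script of the desk interview.
3. Reword the staff e-mail so that it asks for women who meet all inclusion criteria and none of the exclusion criteria, and list the latter.
4. Reconcile the surgery criterion across section 7.2, the desk interview, Q9/Q10 and Table 1, and state what is done with a respondent who reports surgery.

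Cost: a few RedCap fields with branching, a sentence or two in the e-mail, a short edit to sections 7.2 and 8 and Table 1, and slightly fewer staff forms. It has to be done before the link is sent.
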